A. Description of the of the procedures for the double blind placebo controlled arm

Day 1) Phone screening

During an initial telephone conversation, we will provide a brief description of the study, do an initial screening of the subject to ensure that they meet inclusion criteria and do not possess any of the exclusion criteria, and schedule the subject's intake session.

Day 2) Intake session

Subject comes to The John B Pierce Laboratory where written informed consent will be obtained. The subject will be asked to refrain from alcohol use the day before any session. The subject then completes a subset of the following intake measures to determine eligibility:

A. Toxicology/pregnancy screening

We will perform the following screens:

- i. Breath alcohol levels will be assessed with the Alcohawk Elite Breathalyzer.
- ii. Urine toxicology screens will be conducted using the Integrated E-Z Split Key Cup II (Innovacon Inc., San Diego, CA) for opiates, cocaine, THC, PCP and barbiturate.
- iii. We do not wish to study females who may be pregnant. Therefore, all females of childbearing potential will be given a urine pregnancy test.

If a subject tests positive on any of these screens they will be informed of the result and excluded from further participation in the study. The results from these tests will not be recorded for subjects who are excluded for positive results.

Genotyping:

We will collect a saliva sample to genotype for SNPs related to dopaminergic and opiate signaling in the brain. The gene loci tested and their SNPs are attached.

Iowa Gambling Game:

Iowa Gambling Task³¹: Designed to evaluate the ability to postpone immediate reward for a longer-term successful outcome, tests emotional decision-making ability. Subjects play a card game under conditions of limited knowledge about reward and penalty. The participant is presented with 4 decks of card. Two decks are advantageous (A and B); A and B do not give big gains but do not lead to losses after 100 draws. Two decks are disadvantageous (C and D). C

and D give big gains but end up leading to big losses after 100 draws. Patients with inability to delay immediate gratification to improve long-term outcomes perform badly on this task. The gains and losses will be in fake Monopoly money.

Effort Expenditure for Rewards (EEfRT)

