Each participant will meet with [name] to go over the possible side effects of 30 mg of Morphine, 50 mg of Naltrexone and placebo given at one dose. [name] will go over the most common side effects and will emphasize the risk of altered mental status (e.g. sleepiness, drowsiness) after one dose of morphine. [name] is Yale trained psychiatrist and will collect psychiatric history on possible previous misuse of alcohol, illegal drugs and prescription drugs. Any subject with such previous history will be excluded from the study. In addition, each participant will be given a patient information sheet about each of the medications used in the study.

To avoid fatigue subjects will take a 5-minute breaks every 15-20 minutes. This session takes about 2 hours. If the subject meets all eligibility criteria we will schedule them for a Presupplementation session at The John B Pierce Laboratory.

Measurment of body fat composition:

We will measure body fat composition of our participants; body fat and body mass index can be confounding in our analysis given that brain response to food is different between obese and healthy weight participants³⁶. The BodPod body composition tracking system is an air displacement plethysmograph which uses whole-body densitometry to determine body composition (fat and fat-free mass). The BodPod is an egg-shaped pod that consists out of two chambers. The front, or Test chamber, is where the subject sits and is comprised of a seat that forms a common wall separating it from the rear, or reference chamber. During the brief data collection period of the volume measurement, the chamber door is secured by a series of electromagnets and a gasket. A diaphragm is mounted on the common wall, which oscillates during testing. This causes small changes in volume inside the chamber, of which the pressure response to these small volume changes is measured. This is done by measuring the interior volume of the empty BodPod chamber, then measuring it again when the subject is seated inside. By subtraction, the subject's body volume is obtained. Once the subject's mass and volume are determined, body density is calculated and the relative proportions of fat and fat-free mass are determined. Thus this procedure is entirely non-invasive. A complete test requires about 5

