- Upon arrival to the Magnetic Resonance Research Center (MRRC) participants a urine drug test will be obtained as well as Breath alcohol levels will be assessed with the Alcohawk Elite Breathalyzer. If any of these tests are positive the study will be cancelled. Next, vitals signs (VS)(blood pressure, heart rate, respiratory rate, pulse oximetry, and temperature). If the urine drug test is positive for opiates or methadone the study will be cancelled and the subject disqualified for this study.
- Participants with BP < 90/60 and/or heart rate < 60 will be excluded and the study will be cancelled. VS will be logged in to a VS sheet and kept with the participant paper record in our study binders. Mental and neurologic status will be assessed for a baseline using the National Institutes of Health (NIH) Stroke Scale Neurological Assessment flow sheet (see attached form).
- 3. Next 20 ml of blood will be withdrawn. All blood samples will be placed in pre-chilled test tubes, and centrifuged at 4 C and the plasma stored at -70 C until analyzed according to standard procedures in the YCCI Core Laboratory
- 4. Next, participants will be undergo fMRI scanning: fMRI session: Set up is as above for fMRI simulator in fMRI training. Prior to getting the subject into the MR-room all people involved with the study walk through a detector designed to detect metal objects. We will use a Siemens 3T Trio TIM scanner with a 32channel head-coil. A T1-weighted 3D MPRAGE sequence (4 minutes) will be performed to obtain a high-resolution anatomical image and echoplanar imaging will be used to measure

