The subjects will be healthy human adults, and human adults suffering from pain conditions such as low back pain, knee arthritis, or fibromyalgia with normal gustatory and olfactory function and no medical conditions that would preclude them from being tested in the MR scanner. These subjects will be recruited from the Yale University Community, including undergraduate students, graduate students, and staff, with an age range between 18 and 65 years. Women and minorities will be encouraged to participate in all proposed experiments. We will monitor the subject pool periodically to ensure appropriate representation of all ethnic backgrounds and both sexes.

6. **Subject classification:** Check off all classifications of subjects that will be specifically recruited for enrollment in the research project. Will subjects who may require additional safeguards or other considerations be enrolled in the study? If so, identify the population of subjects requiring special safeguards and provide a justification for their involvement.

Children	🔀 Healthy	Fetal material, placenta, or dead fetus
Non-English Speaking	Prisoners	Economically disadvantaged persons
Decisionally Impaired	Employees	Pregnant women and/or fetuses
Yale Students	Females of ch	nildbearing potential

NOTE: Is this research proposal designed to enroll children who are wards of the state as potential subjects? Yes No (If yes, see Instructions section VII #4 for further requirements)

 Inclusion/Exclusion Criteria: What are the criteria used to determine subject inclusion or exclusion? Inclusion criteria:

NCT04342130

Healthy participants

Patients in pain: suffering from persistent pain more days than not, 3/10 in intensity on a numerical rating scale, for at least 6 weeks or more.

Exclusion criteria: Any DSM diagnosis, diabetes, food allergies, lactose intolerance, participants seeking to quit smoking or to lose weight, participants on any psychotropic medication including opiate based analgesics (e.g. oxycodone, methadone, suboxone), pregnant or nursing women, pacemaker or other implanted electrical devices. Participants with a past history of head trauma or seizures will be excluded. Any past history of illegal drug or alcohol misuse will be an exclusion criterion.

8. How will **eligibility** be determined, and by whom?

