Eligibility will be determined by the research coordinator upon initial telephone contact using a screening form (see attached phone screening form). The form asks general information questions (date of birth, handedness, native language, etc.) and queries the participants about their health and any history of conditions known to affect cognitive functioning (e.g. stroke, medications, head trauma), or any conditions that could compromise the safety of conducting an MRI scan (e.g. claustrophobia, metal in the body, pacemaker). A more lengthy MRI safety screening form will be administered when the participant arrives for the scanning session (see attached MRI screening form) at the Magnetic Resonance Research Center in the Congress Avenue building of Yale School of Medicine. We do not wish to study females who are or may be pregnant. Therefore, as part of our MRI safety screening protocol, all females of childbearing potential will be given a urine pregnancy test prior to scanning. Results of the pregnancy test will be given to them only and will remain confidential. If the results indicate a subject is pregnant she will not participate in the fMRI scan, and will be excluded from the study.

9. **Risks:** Describe the reasonably foreseeable risks, including risks to subject privacy, discomforts, or inconveniences associated with subjects participating in the research.

Risk involved with the questionnaires

It is possible that interviews may cause distress or concern to the participants. One potential risk to participants is that it may be distressing to disclose information about psychiatric difficulties such as previous history of substance misuse. In our estimation, there is a low risk of this possibility and the effects would probably be short lived. We have conducted several hundred of these interviews with no adverse effects. It is possible that subjects may become frustrated with some of the impulsivity or cognitive assessments. We have conducted hundreds of similar cognitive assessments and have had no adverse outcomes.

Risks involved with the mock fMRI scanner

Page 21 of 52

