- Hematologic & oncologic: Anemia (2% to <5%), thrombocytopenia (<2% to <5%), leukopenia (2%), hematocrit decreased
- Hepatic: Increased liver function enzymes
- Hypersensitivity: Hypersensitivity reaction
- Infection: Infection
- Local: Local irritation
- Neuromuscular & skeletal: Back pain (<2% to 10%), asthenia (2%), tremor (2%), arthralgia (<2%), bone pain (<2%), foot-drop (<2%), decreased bone mineral density, muscle rigidity, muscle twitching
- Ophthalmic: Amblyopia (<2%), blurred vision (<2%), conjunctivitis (<2%), diplopia (<2%), miosis (<2%), nystagmus (<2%), eye pain, visual disturbance
- Respiratory: Dyspnea (3% to 10%), flu-like symptoms (<2% to 10%), hypoventilation (<5%), asthma (<2%), atelectasis (<2%), hypoxia (<2%), pulmonary edema (noncardiogenic, <2%), respiratory depression (<2%), respiratory insufficiency (<2%), rhinitis (<2%), hypercapnia
- Miscellaneous: Accidental injury (2% to 10%), fever (2% to 10%)

Side effects at < 1%

• <1% (Limited to important or life-threatening): Anaphylaxis, apnea, biliary tract spasm, bronchospasm, decreased cough reflex, dehydration, disorientation, disruption of body temperature regulation, genitourinary tract spasm, hemorrhagic urticaria, hyperalgesia, hypertonia, increased intracranial pressure, intestinal obstruction, laryngospasm, menstrual irregularities, myoclonus, paradoxical central nervous system stimulation, sepsis, toxic psychoses

Oral Morphine is contraindicated in somebody who has bowel obstruction.

Oral Naltrexone: Oral Naltrexone is prescribed for alcohol and opiate dependence; it is estimated that 221 million prescriptions of Naltrexone were dispensed in 2007⁷⁴. The starting dose is 50 mg daily. Naltrexone has a wide margin of safety. Naltrexone has a low incidence of common adverse events⁷⁵. Naltrexone's FDA-approved label includes a black-box warning regarding hepatotoxicity, although these reversible effects tend to be associated with much higher doses than those used in routine clinical practice (e.g., 300 mg/day or more) and tend to occur only after a patient is on these high doses for extended periods. *For the purpose of our current protocol we will use one 50 mg dose one time only.* In addition, there is no evidence of long-term toxicity associated with the intake of one dose of Naltrexone. Naltrexone side effects occurring at > 10% rate are reported for combined oral and injectable form; however, as mentioned above oral Naltrexone has a low risk of side effects.

>10%:

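### The protocol calls bowel obstruction a contraindication to oral morphine, but neither its exclusion criteria nor any described check names it (minor safety fix)

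*Combined protocol and SAP*

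**What the plan says.** The background on oral morphine in Section VI.A.2 ends with an unqualified statement: "Oral Morphine is contraindicated in somebody who has bowel obstruction".

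The exclusion criteria in Section V, item 7 open with "Any DSM diagnosis, diabetes, food allergies, lactose intolerance, participants seeking to quit smoking or to lose weight". They go on to psychotropic and opioid medication, pregnancy and nursing, implanted electrical devices, head trauma, seizures, and past drug or alcohol misuse. The pain group is admitted if "suffering from persistent pain more days than not, 3/10 in intensity on a numerical rating scale", for at least 6 weeks. Section V, item 5 adds example conditions (low back pain, knee arthritis, fibromyalgia) and requires normal taste and smell and no medical bar to MR scanning. The open-label arm (Section V, item 3.B) takes 15 patients with chronic low back pain.

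Eligibility is settled first by telephone. Staff are to "do an initial screening of the subject to ensure that they meet inclusion criteria and do not possess any of the exclusion criteria" (Section V, item 3.A, Day 1). According to Section V, item 8, the research coordinator does this with a form that "queries the participants about their health and any history of conditions known to affect cognitive functioning" and that also covers MRI safety.

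**The concern.** A protocol that names a contraindication to one of its own drugs would normally turn it into an exclusion. This protocol does so for other hazards. Food allergy, pregnancy and pacemakers all appear under Risks (Section V, item 9) and again among the exclusions in item 7. The one contraindication stated for morphine does not.

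The gap matters because the dose offers the participant little in return. Section VI.A.7 says the drug is given to study brain activity and not treatment effects, and Section IX claims no direct benefit. Section X.1 allows only that pain participants might feel short-term relief. There is therefore little to set against dosing someone whom the protocol itself says should not receive oral morphine.

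**Working it through.** The protocol states no figure to reproduce. The check is a comparison of the stated contraindication with each place where it could take effect.

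1. **Exclusion list (Section V, item 7).** It contains no bowel or gastrointestinal obstruction and no general clause on contraindications to the study drugs. The only broad medical clause, in item 5, concerns fitness for MR scanning.
2. **Pain-group definition (items 5 and 7).** The example conditions and the rules on pain frequency, intensity and duration do not rule obstruction out. The label of healthy participant plausibly does for the control group, so the gap mainly concerns patients.
3. **Phone screen (item 3.A, Day 1; item 8).** It tests people against the listed criteria, so an unlisted condition triggers nothing. The form asks about health in general, but the topics named are cognitive conditions and MRI safety.
4. **Intake tests (item 3.A, Day 2).** These are breath alcohol, urine toxicology and pregnancy.
5. **Physician meeting at intake (item 3.A).** The physician goes over side effects and "will collect psychiatric history on possible previous misuse of alcohol, illegal drugs and prescription drugs". In addition, "each participant will be given a patient information sheet about each of the medications used in the study". No bowel history is mentioned.
6. **Dosing day (item 3.A, Day 3).** The checks are urine drug test, breath alcohol, vital signs and a stroke-scale baseline. The vital-sign stop rule is "Participants with BP < 90/60 and/or heart rate < 60 will be excluded and the study will be cancelled". Nothing concerns the bowel.
7. **Medical and surgical history (item 10, MRI risks).** It is described only as the means of excluding MRI hazards.
8. **Self-reported medical illness (Section VIII, item a).** It is collected as research data, with no rule attached.
9. **Other mentions of the condition.** Section VI.A.2 lists paralytic ileus and intestinal obstruction as possible side effects of morphine. Neither is a check before dosing.

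**What lowers the risk.** Each pre-dose scan has two 9.6-minute milkshake runs and two 9.6-minute sucrose runs: (2 + 2) × 9.6 = 38.4 minutes. A 10-minute mock run takes place at intake. These runs are an imaging task with deliveries of 0.75 cc each and not a test for obstruction, but a person with active, symptomatic obstruction is unlikely to get through them.

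**How often an added question would be asked.**
- Crossover participant: 1 intake + 3 dosing visits (Days 3, 4 and 5) = 4.
- Open-label participant: 1 intake + 1 visit = 2, or 1 + 2 = 3 if the two scan sessions in the open-label payment table (Section X, item 2) are separate visits.

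**The case against.** The best case against the point is that the protocol does ask about health. The phone form asks about it, a medical and surgical history is taken at screening, and self-reported medical illness is recorded. Any of these could bring an abdominal problem to light. The phone form is an attachment that could not be read and may already contain the question. Information sheets describe each drug, the phone call covers medications and risks (Section VII, consent process), and orders go through the hospital drug service (Section VI.A.6). The investigators also affirm that the study population does not significantly raise drug risk (Section VI.A.1, Exempt Category 1). The example pain conditions are musculoskeletal or widespread, not abdominal. The single 30 mg dose lies within the 10 to 30 mg starting range in Section VI.A.2, and the study physician stays throughout drug visits (Section V, item 10).

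All of this is accurate, and it is why the practical risk is very low. It also disposes of a stronger inference that a reader might draw, namely that participants are dosed without anyone asking about their health. The text describes three general health inquiries and leaves the content of the main form unseen, so that reading is not supported.

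What remains is narrower. No described step names the condition, and no written rule tells staff to exclude on it. If the form does ask, the coordinator still has no criterion on which to act. The physician is present, but the protocol does not direct the physician to ask.

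**Conclusion.** The point holds as a minor safety gap. The protocol states a contraindication to a study drug and does not carry it into eligibility or into any described check. Confidence is high for that statement about the text. It does not extend to what staff ask in practice, because the attached phone form and information sheets were not available.

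The risk cannot be quantified, since the documents give no frequency of bowel obstruction. It is judged very low, on the assumption that ambulatory volunteers who complete the tasting runs are unlikely to have active obstruction when dosed.

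Two further readings should be resisted. The protocol does not contradict itself: the eligibility list is incomplete, and nothing in it says that such patients may be dosed. Nor does the gap bear on the statistics. Sample size, the repeated-measures comparison and the imaging outcomes are unaffected, and very few people would be excluded by the change.

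**What to change.** Add to the exclusion criteria in Section V, item 7, for both the double-blind and the open-label arm: *known or suspected bowel obstruction, or any other contraindication to morphine or naltrexone*. Have the study physician confirm this at the existing intake meeting, and add one brief question to the existing pre-dose checks. In the double-blind arm, ask it at all three dosing visits, because the drug given that day is concealed.

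The cost is one line of text and a short question at contacts that already take place: about 4 times per crossover participant, and 2 to 3 times per open-label participant depending on how the two scan sessions are scheduled. Extra exclusions should be negligible in number.

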Prior to obtaining consent, all participants will be screened on the phone by the research coordinator at The John B Pierce Laboratory. During this conversation, the research coordinator will provide a brief description of the study, including information about tasks the subject will have to perform in the behavioral assessments, where the study is conducted, the medications used, the risks and benefits of paricipation, how long the entire study participation will take, and the amount of financial compensation. Subjects will also be screened to ensure that they meet inclusion criteria and do not possess any of the exclusion criteria. If the subject is eligible and willing to participate, the first session will be scheduled. Informed consent will be obtained immediately at the beginning of the first session. Personnel obtaining consent have a thorough understanding of the methodology of the protocol and a comprehensive knowledge of the procedures of the protocol and are capable of answering the possible questions raised by the potential subject regarding the study. A subject will sit down at a desk in a room. The study personnel will ask the subject to read through the entire compound research authorization and consent form. After the subject had read the entire form the researcher will verbally summarize the procedure, risks and steps taken to minimize risks. The subject is explicitly asked if they have any questions. All questions will be answered, except in the rare case that providing full disclosure may influence the outcome of the study (e.g. we do not want subjects to be aware that the puddings are manipulated in fat content). In these circumstances, the experimenter will explain that this is the case and offer to provide a fuller answer after the experiment. Subjects will receive additional details about the assessments they are to perform and will be informed that they may withdraw from the study at any time with no penalty. Subjects will be asked if they understand what the study entails and if they have had sufficient opportunity to consider whether or not to participate. If a subject affirms she/he will then be asked to sign the compound consent form and research authorization form and given a copy (attached).

10. Evaluation of Subject(s) Capacity to Provide Informed Consent/Assent: Indicate how the personnel obtaining consent will assess the potential subject's ability and capacity to consent to the research being proposed.

This research does not involve subjects with limited decision-making capacity. We will not recruit vulnerable subjects. For this reason we do not anticipate recruiting subjects without the ability and capacity to consent. However, we will ask subjects if they understand what the study entails and if they have had sufficient information and opportunity to consider whether or not to participate.

11. Documentation of Consent/Assent: Specify the documents that will be used during the consent/assent process. Copies of all documents should be appended to the protocol, in the same format that they will be given to subjects.

Adult compound consent and research authorization forms are attached.

12. Non-English Speaking Subjects: Explain provisions in place to ensure comprehension for research involving non-English speaking subjects. If enrollment of these subjects is anticipated, translated copies of all consent materials must be submitted for approval prior to use.

Our research does not involve non-English-speaking subjects.

12(a) As a limited alternative to the above requirement, will you use the short form* for consenting process if you unexpectedly encounter a non-English speaking individual interested in study participation and the translation of the long form is not possible prior to intended enrollment?

YES \square NO \square

Note* If more than 2 study participants are enrolled using a short form translated into the same language, then the full consent form should be translated into that language for use the next time a subject speaking that language is to be enrolled.

Several translated short form templates are found on our website at: http://www.yale.edu/hrpp/forms-templates/biomedical.html. If the translation of the short form is not available on our website, then the translated short form needs to be submitted to the IRB office for approval via amendment prior to enrolling the subject. *Please review the guidance and presentation on use of the short form available on the HRPP website.*

If using a short form without a translated HIPAA Research Authorization Form, please request a HIPAA waiver in the section above.

13. Consent Waiver: In certain circumstances, the HIC may grant a waiver of signed consent, or a full waiver of consent, depending on the study. If you will request either a waiver of consent, or a waiver of signed consent for this study, complete the appropriate section below.

- Requesting a waiver of signed consent
- **Requesting a full waiver of consent**

Page 42 of 52

A. Waiver of signed consent: (Verbal consent from subjects will be obtained. If PHI is	is
collected, information in this section must match Section VII, Question 6)	
Requesting a waiver of signed consent for Recruitment/Screening only	
If a superior of size of size of a superior data and the set of th	

If requesting a waiver of signed consent, please address the following:

a. Would the signed consent form be the only record linking the subject and the research? Yes No

b. Does a breach of confidentiality constitute the principal risk to subjects?

Yes No

OR

c. Does the research activity pose greater than minimal risk?

Yes *If you answered yes, stop. A waiver cannot be granted.* Please note:

Recruitment/screening is generally a minimal risk research activity

AND

d. Does the research include any activities that would require signed consent in a non-research context? Yes No

Requesting a waiver of signed consent for the Entire Study (Note that an information sheet may be required.)

If requesting a waiver of signed consent, please address the following:

a. Would the signed consent form be the only record linking the subject and the research? Yes No

b. Does a breach of confidentiality constitute the principal risk to subjects?

OR

AND

d. Does the research include any activities that would require signed consent in a non-research context? Yes No

B. Full waiver of consent: (No consent from subjects will be obtained for the activity.)

Requesting a waiver of consent for Recruitment/Screening only

a. Does the research activity pose greater than minimal risk to subjects?

Yes *If you answered yes, stop. A waiver cannot be granted.* Please note:

Recruitment/screening is generally a minimal risk research activity

b. Will the waiver adversely affect subjects' rights and welfare? Yes No

c. Why would the research be impracticable to conduct without the waiver?

d. Where appropriate, how will pertinent information be returned to, or shared with subjects at a later date?

NCT04342130

Requesting a full waiver of consent for the Entire Study (Note: If PHI is collected, information here must match Section VII, question 6.)

If requesting a full waiver of consent, please address the following:

a. Does the research pose greater than minimal risk to subjects?

Yes If you answered yes, stop. A waiver cannot be granted.

No

b. Will the waiver adversely affect subjects' rights and welfare? Yes No

c. Why would the research be impracticable to conduct without the waiver?

d. Where appropriate, how will pertinent information be returned to, or shared with subjects at a later date?

SECTION VIII: PROTECTION OF RESEARCH SUBJECTS

Confidentiality & Security of Data:

a. What protected health information (medical information along with the HIPAA identifiers) about subjects will be collected and used for the research?

Information about (self-reported) alcohol consumption, drug use, medical illness, major psychiatric illness, genetic information, brain images and use of medications will be collected.

c. How will the research data be collected, recorded and stored?

Data will consist of verbal, written, or computerized ratings of sensory stimuli, questionnaires, and computerized responses to the neuropsychological and impulsivity assessments. All data will be kept confidential. Participant information is maintained in computer files that are password protected, and data from individuals (computer files and hard copy versions) are identified only by code. Only the primary investigator and research staff, the Yale HIC, and the National Institute of Health, which sponsors the study, will have access to these files. The data will be archived in the same manner after the research is completed. Seven years after completion of the study the identifying data will be deleted by zeroing with software as in accordance with policies and procedures as determined by Yale University (procedures 1609 and 1610).

c. How will the digital data be stored? ⊠ CD ⊠ DVD □ Flash Drive □ Portable Hard Drive ⊠ Secured Server ⊠ Laptop Computer □ Desktop Computer ⊠ Other

The database with subject identifiers and means to link subject names and codes with research data is stored in a database in a separate location on a secured server at The John B Pierce Laboratory. Access to the database itself is password protected. Hardcopy PHI

Page 44 of 52

NCT04342130

data is in a locked cabinet. All other digital media (CD, DVD, Laptop computers) only contain research data that are identified by code.

d. What methods and procedures will be used to safeguard the confidentiality and security of the identifiable study data and the storage media indicated above during and after the subject's participation in the study?
Do all portable devices contain encryption software? Yes No If no, see http://hipaa.yale.edu/guidance/policy.html

None of the portable devices contain PHI or HIPAA identifiers, and they are password protected. The identifying data is stored on a password protected database on a secure server in The John B Pierce Laboratory. Thus identifiers are not kept on the same device as the study information.

d. What will be done with the data when the research is completed? Are there plans to destroy the identifiable data? If yes, describe how, by whom and when identifiers will be destroyed. If no, describe how the data and/or identifiers will be secured.

Identifying data are retained for a period of seven years after publication.

e. Who will have access to the protected health information (such as the research sponsor, the investigator, the research staff, all research monitors, FDA, Yale Cancer Center Data and Safety Monitoring Committee (DSMC), SSC, etc.)? (please distinguish between PHI and de-identified data)

As NIH is funding the study, rules governing NIH access will apply. No other entities besides research staff and the investigator will have access to PHI or de-identified data, with the exception of presentations of data. These are typically reported as group averages. Where individual data are reported, individuals are not identified except by code.

g. If appropriate, has a Certificate of Confidentiality been obtained? N/A

h. Are any of the study procedures likely to yield information subject to mandatory reporting requirements? (e.g. HIV testing – reporting of communicable diseases; parent interview - incidents of child abuse, elderly abuse, etc.). Please verify to whom such instances will need to be reported. N/A

SECTION IX: POTENTIAL BENEFITS

Potential Benefits: Identify any benefits that may be reasonably expected to result from the research, either to the subject(s) or to society at large. (Payment of subjects is not considered a benefit in this context of the risk benefit assessment.)

There are no direct benefits to participating subjects. However, the study will help us understand the brain response to food in the presence and absence of opiate agonist/antagonists, which are highly prescribed nowadays for pain, addiction and obesity. This understanding in turn will help us study the effect on body weight and behavior of prescription opiates in patients with pain.

SECTION X: RESEARCH ALTERNATIVES AND ECONOMIC CONSIDERATIONS

1. Alternatives: What other alternatives are available to the study subjects outside of the research?

The healthy participants for this study are not in need of treatment or seeking treatment. For this reason there is no alternative, except to decline participation in the study. The pain participants might feel short-term relief of pain; If patients are interested in seeking such treatment they will be asked to talk to their doctor about it.

2. **Payments for Participation (Economic Considerations):** Describe any payments that will be made to subjects, the amount and schedule of payments, and the conditions for receiving this compensation. The subject's payments for the open label and the randomized controlled study are the same per session completed.

Remuneration is as follows for the randomized controlled study:

Type session:	payment:	frequency	Total
behavioral assessment	\$ 80	x 1	= \$80
fMRI scan with milkshake	\$ 100 *	x 3	= \$ 300
Computer Games	\$100	x 1	= 100
-		Subtotal:	$= \frac{380}{380}$
Completion Bonus	\$ 50	x 1	$=$ $\frac{50}{50}$
Accumulated Earnings Bonus		x 1	$=$ $\sqrt[6]{Variable}$
ç		Total payment:	= \$ 530

And for the open label study:

Type session:	payment:	frequency	Total
behavioral assessment	\$ 80	x 1	= \$ 80
fMRI scan with milkshake	\$ 100 *	x 2	= \$ 200
Computer Games	\$100	X	= \$100
		Subtotal:	= \$ 280
Accumulated Earning Bonus	\$		= \$ variable
Completion Bonus	\$ 50		= \$ 50

Total payment: = \$ 430

NCT04342130

* If the subject spends up to 15 minutes in the scanner but do not complete the study, they will instead be paid \$50. If the subject spends more than 15 minutes, they will receive the full \$100 regardless of study completion.

Subjects will participate in one Intake Session (\$80), 3 fMRI scanning sessions (with milkshake, each \$100), and a completion bonus of \$50, leading to a maximal remuneration of \$430. In addition to this, they make variable earnings depending on their performance on one of the computer tasks.

3. **Costs for Participation (Economic Considerations):** Clearly describe the subject's costs associated with participation in the research, and the interventions or procedures of the study that will be provided at no cost to subjects.

There are no costs to the subject.

- 4. In Case of Injury: This section is required for any research involving more than minimal risk.
